7.4.1 Off-Site Unanticipated Serious Adverse Device Effect Reporting

[figure not shown]
When participating in multicenter clinical investigations, Investigators may receive off-site USADE reports. These are Sponsor reports of USADEs which occurred at other clinical sites for the same trial, or in different trials using the same test article, that met the criteria for reporting to a regulatory agency. These should be reported to the reviewing IRB within 10 working days or per their established reporting procedures, whichever is shorter.

7.4.2 Reporting Device Deficiencies

A device deficiency is defined as an inadequacy of a medical device with respect to its identity, quality, durability, reliability, safety, or performance. Device deficiencies include malfunctions, use errors, and inadequate labeling.

Investigators must evaluate, record, and report via applicable forms any complaints/deficiencies or malfunctions experienced with the study solution during this trial to the Medical Monitor promptly. The Sponsor and Medical Monitor shall review all device deficiencies and, upon the Sponsor's request, Investigators must supply any additional information related to the safety reporting of a particular event.

Report device deficiencies within 24 hours of knowledge to:

The Medical Monitor will distribute, within 24 hours of knowledge, all device deficiencies to the Sponsor including: [REDACTED]

The Sponsor shall review all device deficiencies and determine and document in writing whether they could have led to an SAE. In the event of a disagreement between the Sponsor and the Investigator(s), the Sponsor shall communicate both opinions to the reviewing IRB per their established reporting procedures and the health authority.

7.4.3 Guidelines for Reporting Pregnancies

All female subjects of childbearing potential must use an effective method of birth control during the study, to include 2 weeks after last visit, in a manner such that risk of contraceptive failure is minimized. Abstinence is allowed as a birth control method.

Study #932 - Protocol

[figure not shown]
During the study, all female subjects of childbearing potential should be instructed to contact the Investigator immediately if they suspect they might be pregnant (eg. missed or late menstrual period). Female subjects who become pregnant during the study will be followed until completion of pregnancy. Every effort will be made to obtain the health status of the mother and infant or fetus (in cases of miscarriage or therapeutic abortion) at term. Pregnancy itself is not considered an AE.

All confirmed pregnancies must be reported on a paper Pregnancy Report Form and submitted to the Medical Monitor via facsimile or email transmission within 24 hours of the Investigator's awareness of the pregnancy. The Medical Monitor will distribute the completed form to the Sponsor as per the distribution list in Section 7.4.

All pregnancies will be followed until outcome even after study closure. The outcome of all pregnancies will be reported on a paper Pregnancy Outcome Report Form and submitted to the Medical Monitor via facsimile or email transmission once the outcome is learned. The Medical Monitor will distribute the completed form to the Sponsor as per the distribution list in Section 7.4.

Although pregnancy occurring in a clinical study is not considered to be an AE or SAE, any pregnancy complication, spontaneous abortion, or elective termination of a pregnancy, for medical reasons, will be recorded as an SAE. Any serious complication or event resulting from the pregnancy should be reported to the Medical Monitor within 24 hours on the SAE or Significant Non-Serious AE Report Form along with the Pregnancy Report Form.

The contact for reporting pregnancies and pregnancy outcomes are:

8.0 STATISTICAL METHODS

8.1 Study Endpoints

8.1.1 Primary Effectiveness Endpoints

- a. Overall comfort averaged over all follow-up visits.
- b. Dryness averaged over all follow-up visits.
- c. Lens deposits at all follow-up visits.

8.1.2 Secondary Effectiveness Endpoints

There are no secondary effectiveness endpoints.

8.1.3 Primary Safety Endpoint

Slit lamp findings greater than Grade 2.

8.2 Hypotheses

8.2.1 Overall Comfort Averaged Over All Follow-up Visits

The null hypothesis (H_0) is that the difference in mean overall comfort (test group mean [μ_T] minus standard group mean [μ_S]) is less than or equal to negative five points. The alternative hypothesis (H_1) is that the difference is greater than negative five points.

$$H_0: \mu_T - \mu_S \leq -5$$

$$H_1: \mu_T - \mu_S > -5$$

8.2.2 Dryness Averaged Over All Follow-up Visits

The null hypothesis (H_0) is that the difference in mean dryness score (test group mean [μ_T] minus standard group mean [μ_S]) is less than or equal to negative five points. The alternative hypothesis (H_1) is that the difference is greater than negative five points.

$$H_0: \mu_T - \mu_S \leq -5$$

$$H_1: \mu_T - \mu_S > -5$$

8.2.3 Lens Deposits at All Follow-up Visits

The null hypothesis (H_0) is that the difference in the proportion of eyes with None or Light ratings of lens deposits at all Follow-up Visits (test group proportion [r_{TT}] minus standard group proportion [r_{SS}]) is less than or equal to -0.1 (-10%). The alternative hypothesis (H_1) is that the difference is greater than -0.1 (-10%).

$$H_0: r_{TT} - r_{SS} \leq -0.1$$

$$H_1: r_{TT} - r_{SS} > -0.1$$

8.2.4 Slit Lamp Findings Greater than Grade 2

The null hypothesis (H_0) is that the difference in the proportion of eyes with slit lamp findings greater than grade 2 (test group proportion [r_{TT}] minus standard group proportion [r_{TS}]) is greater than or equal to 0.05 (5%). The alternative hypothesis (H_1) is that the difference is less than 0.05 (5%).

$$H_0: r_{TT} - r_{TS} \geq 0.05$$

$$H_1: r_{TT} - r_{TS} < 0.05$$

8.3 Sample Size

Estimates of standard deviations and proportions were obtained from Bausch + Lomb Study #872.¹

The sample size calculations assume that the level of analysis will be the eye and that the outcomes from each subject's eyes will be independent.

Sample size calculations were completed using nQuery Advisor® 7.0 software.

8.3.1 Overall Comfort

When the sample size in each group is 226, a two group 0.025 one-sided t-test will have 96.82% power to reject the null hypothesis that the test is not non-inferior to the standard (the difference in means, $\mu_{TT} - \mu_{TS}$, is -5 or farther from zero in the same direction) in favor of the alternative hypothesis that the test is non-inferior, assuming that the expected difference in means is 0 and the common standard deviation is 13.9.

8.3.2 Dryness

When the sample size in each group is 226, a two group 0.025 one-sided t-test will have 96.62% power to reject the null hypothesis that the test is not non-inferior to the standard (the difference in means, $\mu_{TT} - \mu_{TS}$, is -5 or farther from zero in the same direction) in favor of the alternative hypothesis that the test is non-inferior, assuming that the expected difference in means is 0 and the common standard deviation is 14.0.

8.3.3 Lens Deposits

With 226 eyes in each group, the lower limit of the observed one-sided 97.5% confidence interval will be expected to exceed -0.100 with 97.38% power when the Standard proportion, π_{TS} , is 0.925 and the Test expected proportion, π_{TT} , is 0.925; results are based on 100,000 simulations using the Newcombe-Wilson score method to construct the confidence interval.²

8.3.4 Slit Lamp Findings Greater than Grade 2

With 226 eyes in each group, the upper limit of the observed one-sided 97.5% confidence interval will be expected to be less than 0.050 with 99.00% power when the Standard proportion, π_{TS} , is 0.005 and the Test expected proportion, π_{TT} , is 0.005; results are based on 100000 simulations using the Newcombe-Wilson score method to construct the confidence interval.²

8.3.5 Overall Power

If the four primary endpoints are independent, the overall power of the study is 96.82% x 96.62% x 97.38% x 99.00% = 90.18%.

8.3.6 Enrollment Target

Allowing for up to 10% losses, the enrollment target in each treatment group will be $r113 \div (1 - 0.1)1 = 126$. Consequently, the total enrollment target will be approximately 252 subjects (504 eyes).

8.4 Randomization

Subjects will be randomized to one of two treatment arms in a 1:1 ratio, using Test solution or Control solution for the duration of the study. Randomization will be managed using ORS. The randomization will be stratified by lens group within investigational site. The lens group will be determined by the subjects' habitual lens material at baseline and will be one of the groups shown in Table 1 above (page 9).

Efforts will be made to enroll subjects in at least four of the lens strata within each site to minimize confounding between site and lens strata. It should be noted that while the target enrollment for each lens strata is approximately 50 subjects (approximately 25 per treatment arm), some lens strata may be difficult to enroll.

An unmasked statistician who is not otherwise involved in the trial will create the randomization schedule.

8.5 Study Populations

8.5.1 Intent-to-Treat (ITT) Population

The ITT Population will consist of all randomized subjects for subject level summaries and, for eye level summaries, both of their eyes. Subjects will be included in ITT Population summaries according to the treatment group to which they were randomly assigned.

8.5.2 Per Protocol (PP) Population

The PP population will be the primary population used for analysis of the primary effectiveness endpoints. The PP Population will consist of all ITT Population subjects without important (major) protocol deviations for subject level summaries and, for eye level summaries, both of their eyes. Important protocol deviation categories are defined in Section 8.6.4 below (page 41). Subjects will be included in PP Population summaries according to the treatment group to which they were randomly assigned. The PP population will be determined prior to study unmasking.

8.5.3 Safety Population

The Safety Population will consist of all dispensed subjects and, for eye level summaries, both of their eyes. Subjects will be included in Safety summaries according to the treatment that they received. If a subject receives more than one treatment and one of those treatments is the Test solution, then the subject will be included in Safety Population summaries under the Test treatment group.

8.6 Statistical Analysis

8.6.1 Methods of Analysis

8.6.1.1 General Methods

Continuous data will be summarized using descriptive statistics: sample size (n), mean, standard deviation (SD), median, minimum and maximum. Categorical data will be presented using the total counts for each category and corresponding percentages. The denominator for each percentage will be the number of subjects or eyes with non-missing data at the given visit for each respective study treatment, unless otherwise indicated.

As is customary for contact lens solution trials, eyes will be treated as independent sampling units in eye level analyses unless otherwise noted.

Further details will be provided in a separate statistical analysis plan which will be completed and approved prior to unmasking of the treatment assignments.

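### Subjects are randomised, but every primary limit treats a subject's two eyes as independent; if fellow eyes correlate beyond site and lens group, the comfort, dryness and deposits limits are too narrow and 90.18% power is too high

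*Combined protocol and SAP*

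**What the plan says.** **Randomised unit.** Section 8.4: "Subjects will be randomized to one of two treatment arms in a 1:1 ratio". It adds: "The randomization will be stratified by lens group within investigational site". The Objective (Section 2.0) has each subject use the assigned solution bilaterally.

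**Eyes come and go in pairs.** The Per Protocol set (8.5.2) takes ITT subjects "without important (major) protocol deviations for subject level summaries and, for eye level summaries, both of their eyes". Section 8.5.3: "The Safety Population will consist of all dispensed subjects and, for eye level summaries, both of their eyes". Under Section 3.2.3 a subject must leave the study when one eye is discontinued.

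**Sample size.** Section 8.3: "The sample size calculations assume that the level of analysis will be the eye". The same sentence takes the outcomes of a subject's two eyes to be independent. The 226 per group in 8.3.1 to 8.3.4 are eyes; 8.3.6 starts from 113 subjects per group and inflates to 126. Section 8.3.5: "If the four primary endpoints are independent, the overall power of the study is 96.82% x 96.62% x 97.38% x 99.00% = 90.18" percent.

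**Analysis.** Section 8.6.1.1: "As is customary for contact lens solution trials, eyes will be treated as independent sampling units in eye level analyses unless otherwise noted". The comfort model (8.6.1.2, reused for dryness in 8.6.1.3) is an eye-level ANOVA with treatment and site only. Deposits (8.6.1.4) and slit lamp findings (8.6.1.5) use eye-level Newcombe-Wilson limits. Subject ID appears only in the imputation for the ITT sensitivity analysis, not in the model that yields the limit.

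**The concern.** The 226 eyes per arm are 113 randomised subjects. One person scores the comfort and dryness of both eyes, wears the same lens brand in both (inclusion criterion 8), and follows one care routine with one solution. Positive correlation between fellow eyes is therefore plausible on the plan's own facts, and the only reason given for ignoring it is custom.

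In a non-inferiority trial the direction matters. A limit that is too narrow makes it easier to declare an inferior solution non-inferior. All four primary decision rules use such limits, and the sample size rests on the same assumption.

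Stratification qualifies this. Randomisation balances lens group within site, and site is in the ANOVA. Only the correlation that remains within those strata inflates the error.

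**Working it through.** **Inputs.** From 8.3.1 to 8.3.6: 226 eyes (113 subjects) per arm; one-sided alpha 0.025; SD 13.9 (comfort) and 14.0 (dryness), margin -5, true difference 0; deposits 0.925 in both arms, margin -0.10; slit lamp 0.005 in both arms, margin 0.05; 10% losses. Assumed: rho = 0.3, 0.5, 0.9, and the share of variance lying in the strata.

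**1. The plan's figures at rho = 0.** Comfort SE = 13.9 x sqrt(2/226) = 1.308, and 5/1.308 = 3.824; the noncentral t gives 96.82% (stated 96.82%). Dryness gives 96.63% (96.62%). Exact enumeration gives 97.35% for deposits (97.38%) and 99.77% for slit lamp (99.00%). The stated powers multiply to 0.9682 x 0.9662 x 0.9738 x 0.9900 = 0.902. Enrolment is 113/0.9, rounded up to 126 per arm. The arithmetic is sound under its own assumption.

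**2. Variance.** A two-eye mean has variance SD^2 x (1+rho)/2, so an arm mean over 113 subjects has SD^2 x (1+rho)/226. The plan uses SD^2/226. With no variance in the strata, the variance is understated by the factor 1+rho.

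**3. One-sided error of the planned limits, no strata variance.** Comfort and dryness: 1 - Phi(1.96/sqrt(1+rho)). Deposits (0.825 vs 0.925) and slit lamp (0.055 vs 0.005): exact distribution of correlated eye pairs, 113 per arm.

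| rho | Comfort, dryness | Deposits | Slit lamp |
|---|---|---|---|
| 0 | 0.025 | 0.025 | 0.018 |
| 0.3 | 0.043 | 0.043 | 0.032 |
| 0.5 | 0.055 | 0.055 | 0.043 |
| 0.9 | 0.078 | 0.078 | 0.069 |

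Simulating the treatment-plus-site ANOVA puts comfort and dryness slightly higher, up to 0.046 / 0.056 / 0.083. The slit lamp error passes 0.025 at rho about 0.16 with 113 subjects per arm, or about 0.13 if the Safety Set keeps all 126.

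**4. Effect of strata.** Suppose site and lens group explain 15% of comfort variance (assumed: 5% and 10%). Simulated error is then about 0.022 at rho 0.15, 0.032 at 0.3, 0.042-0.047 at 0.5 and 0.072 at 0.9. Correlation arising only from site gave 0.026, and only from lens group 0.017, so neither alone inflates the error. For deposits with about 2% of variance in strata, error is 0.040 / 0.052 / 0.077.

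**5. Pass probability of the planned analysis, true difference zero, no strata variance.** Comfort: Phi((3.824 - 1.965)/sqrt(1+rho)), and likewise for dryness; the other two by enumeration. The factors below are comfort, dryness, deposits and slit lamp.
- rho 0.3: 0.9485 x 0.9459 x 0.9554 x 0.9927 = 85.1%
- rho 0.5: 0.9354 x 0.9326 x 0.9435 x 0.9892 = 81.4%
- rho 0.9: 0.9112 x 0.9080 x 0.9214 x 0.9856 = 75.1%

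If the comfort and dryness statistics correlate 0.7 (assumed), these become 86.8 / 83.6 / 78.1%.

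**6. Power of a valid subject-level analysis, 113 per arm, no strata variance.** For dryness the SE is 14.0 x sqrt((1+rho)/2) x sqrt(2/113) = 1.502 / 1.613 / 1.815, giving 91.2 / 87.0 / 78.3%. Deposits: 92.5 / 88.8 / 79.7%. Joint power by the plan's product rule is 75-77 / 65-66 / 44-46%, the range reflecting 113 or 126 subjects per arm for slit lamp. With comfort and dryness correlated 0.7 it is 78-79 / 69-70 / 50-51%. With 15% of variance in strata, dryness alone is 94.6 / 90.5 / 80.8%.

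**7. Sample size to keep the stated comfort and dryness powers.** 113 x (1+rho) evaluable subjects per arm: at rho 0.5, 113 x 1.5 = 169.5, so 170, or 170/0.9 = 189 with losses.

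**The case against.** **The assumption is disclosed, and a separate SAP is to follow.** Both are true, and the general rule allows exceptions. But 8.6.1.2 to 8.6.1.5 already fix the primary limits and success rules, none makes an exception, and custom does not make a limit valid.

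**The size rests on an assumed rho.** This stands. The direction is firm if correlation remains within strata; the size is not known from these documents. A reader might infer that any positive rho invalidates all four limits. It does not: comfort error is about 0.022 at rho 0.15 if strata hold 15% of the variance, and the slit lamp limit has slack at low rho.

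**The power loss can be overdrawn.** This also stands. A reader might take 44-46% as the power of the protocol as written. That figure belongs to a valid replacement analysis at rho 0.9 with four independent endpoints, a pessimistic combination. The planned analysis passes about 75% of the time there, partly because its limits are too narrow.

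**The dryness ceiling does not always prove overstatement.** Joint power cannot exceed dryness alone, but at rho 0.3 that ceiling is 91%, and at rho 0.5 with 15% of variance in strata it is 90.5%; both are above 90.18%. In those cases the shortfall depends on how the endpoints correlate.

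**Conclusion.** The point holds as a conditional statement. The randomised unit is the subject, the analysed unit is the eye, and nothing in the documents bridges the two. If rho clearly exceeds what site and lens group explain, the comfort, dryness and deposits limits are anti-conservative, with error about double nominal at rho 0.5 when the strata explain nothing and less when they explain something. The slit lamp limit fails only above rho of about 0.13-0.16.

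The 90.18% is right only at rho 0 and under the product rule. This should be corrected before unmasking, because it touches the decision rule of every primary endpoint. A reader might also infer that the trial must enrol more subjects to be valid. It need not: a two-eye-mean analysis restores error to about 0.025 with the planned subjects. More subjects are needed only to keep the stated power.

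**What to change.** **Analysis, 8.6.1.1 to 8.6.1.5.** State that the subject is the independent unit.
- Comfort and dryness: analyse the two-eye mean, or fit a mixed model with a subject random effect. Include site and also lens group, since both define the randomisation strata. With site alone and 15% of variance in strata, the two-eye-mean error is 0.018-0.020, which is needlessly conservative.
- Deposits: Newcombe-Wilson limit with effective n = eyes/(1 + estimated rho). Its error was 0.022-0.027 in the settings examined.
- Slit lamp: the same limit, with a prespecified conservative rule for sparse events, such as effective n = number of subjects. At a rate of 0.005, at least one arm has no events in about 49% of trials (126 subjects per arm, rho 0: 1 - (1 - 0.995^252)^2) to 67% (113 per arm, rho 0.5), so rho often cannot be estimated. The exact rule is the sponsor's choice. With this one, zero events in both arms at 113 subjects gives an upper limit of 1.96^2/(113 + 1.96^2) = 3.3%, still inside the 5% margin.

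**Sample size, 8.3.1 to 8.3.5.** Restate power for 113 subjects per arm over a stated range of rho, taken from Study #872 if its report allows.

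**Cost.** Protocol and SAP wording and standard software; no new data, and no extra enrolment for valid limits. Stated power falls. The sparse-event rule lowers slit lamp power to about 92-96% at 126 subjects per arm, or 89-90% at 113. Keeping the stated comfort and dryness powers would need about 113 x (1+rho) evaluable subjects per arm, about 170 at rho 0.5.

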8.6.1.2 Overall Comfort

At each follow-up visit, overall comfort will be assessed for each eye on a scale from 0 to 100, with 100 denoting the most favorable response. For each eye, mean overall comfort over all follow-up visits will be computed as the average of the non-missing values over all scheduled follow-up visits. Missing data will not be imputed for the primary analysis. Mean overall comfort over all follow-up visits will be summarized at the eye level by treatment using continuous summary statistics for the Per Protocol Set in a table. A one-sided lower 97.5% confidence limit around the difference in means between the test and control treatment groups, computed using an analysis of variance model including the fixed factor of treatment and the fixed blocking factor of site, will be displayed. If the lower confidence limit is greater than -5.0, then the null hypothesis that the test solution is not non-inferior will be rejected, and the test solution will be statistically successful in this outcome.

As a sensitivity analysis, the ITT Population will be analyzed for this endpoint. Summaries by treatment and a confidence interval around the difference in means will be provided as described above using the available data. Twenty-five imputations of missing overall comfort data will be produced using the Markov chain Monte Carlo (MCMC) method with a seed of 1674236965. The variables used to create the imputed datasets will be the randomized treatment assignments (categorical), the subject identification numbers (categorical), and the overall comfort scores observed at each scheduled visit. The differences and standard errors estimated by imputation will be combined to create an estimated difference and confidence limit.

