6.1.1 Screening/Dispensing Visit

A Screening and Enrollment Log will be provided by the Sponsor to track all consented subjects that the Investigator interviews regarding the study and completed study visits for enrolled subjects. Once the Screening and Enrollment Log is complete and all data is reviewed and confirmed by the field CRA, the Investigator will sign and date the form verifying the documented data is correct. The Investigator will retain a copy (yellow copy) of the original document for their records and the field CRA will submit the original to ClinDatrix.

After obtaining written informed consent, prospective subjects will be screened to determine whether they meet the entry criteria for the study.

The Screening/Dispensing Visit will proceed as follows:

NOTE: All VA measurements MUST be made using a phoropter.

- a. Enter the following information on the next available line of the Screening and Enrollment Log:
 - Subject Number
 - Subject Initials
 - Subject Date of Birth (DOB)
 - Gender
 - Habitual Lens Group
 - Visit 1 (Screening/Dispensing) Date
- b. Collect demographic information and record in the subject's source document.
- c. Collect the following baseline lens/lens care history information and lens wear parameters from the subject and record in the subject's source document:
 - Average daily wearing time
 - Hours lenses worn on the day of this visit
 - Average hours of comfortable wear
 - Current lens brand, sphere power and base curve
 - Current lens care products

- d. Perform the following baseline assessments (without lenses; remove the lenses if the subject wore lenses to the visit) and record in the subject's source document:
 - Spherocylindrical refraction
 - High contrast distance best spectacle-corrected visual acuity (BSCVA)
 - Keratometry
- e. Perform a slit lamp examination (remove the lenses if the subject wore lenses to the visit). Record and sketch any scars and slit lamp findings greater than Grade 2 in the subject's source document.
- f. If the subject continues to be eligible, have the subject complete and initial the following form:
 - The Initial Symptoms/Complaints Form (Worn Lenses Symptoms/Complaints Form), including use of rewetting drops.

Site personnel will transcribe this information to the Visit electronic Case Report Form (eCRF), and will retain the original in the study files.

- g. Complete the Initial Lens Performance Assessment Form (Worn Lenses Performance Rating Scales).

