- h. Dispense three pairs (two for back up only) of the subject's habitual contact lenses. Explain to the subject that the used lenses will be removed at the follow-up visits and returned to the Sponsor.
- i. Instruct subject to insert study lenses.
- j. Instruct subject to complete Symptoms/Complaints Form (Abbreviated version: Study Lenses Symptoms/Complaints).
- k. Complete the Lens Performance Assessment Form (Study Lenses Performance Rating Scales).
- l. Record the following into the subject's source documentation:
 - Dispensed lens type (brand), sphere power, base curve
 - High contrast distance lens VA
 - Over-refraction and distance VA
 - Lens wettability
 - Lens centration
 - Lens movement
 - For each eye, compare the high contrast distance lens VA to the high contrast Distance Best Spectacle-Corrected VA obtained at this visit. If the VA has decreased by 5 letters (0.1 logMAR) or more, explain.

- m. Indicate on the Screening and Enrollment Log whether the subject is a "Screen Pass" or "Screen Fail." Only "Screen Pass" subjects should be randomized in the study. "Screen Fail" subjects are ineligible and cannot be randomized in the study. No eCRFs shall be completed for "Screen Fail" subjects.
 - *If the subject is a "Screen Pass":* Log into ORS to randomize the subject. Enter the subject number from ORS on the Screening and Enrollment Log.

- *If the subject is a “Screen Fail”*: the reason for screen failure must be documented on the Screening and Enrollment Log and in the subject record, and maintained with a copy of their ICF.
- n. If the subject is a “Screen Pass” the Unmasked Designee should then dispense Study Kit bottles 1, 2, 3, and 4 only (keeping bottle 5 as a reserve at the site) (refer to Section 4.4.2) to the subject and record in the subject’s individual Product Accountability Log.
- o. The Unmasked Designee will explain to the subject that:
 - Cartons and bottles are NOT to be opened in front of any other site personnel.
 - The subject should retain all study materials during the course of the study.
 - Prior to coming to the site for the 3-month, exit or early study termination/suspension visits, follow-up visit or exit visit the subject should: (i) place all used and unused study solution bottles into their original white cartons, (ii) place the cartons and all lens cases into the opaque white drawstring return bag, (iii) close the bag, and (iv) return it to the unmasked designee.

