8.6.1.3 Dryness

At each follow-up visit, dryness will be assessed for each eye on a scale from 0 to 100, with 100 denoting the most favorable response. Dryness will be analyzed using the methods described above for overall comfort. The seed for multiple imputation will be 1975251391.

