9.6 Institutional Review Board

The Investigator should ensure that the following are approved by their institution IRB, or if not using their institution's IRB, approved by the reviewing central IRB prior to entering any subjects in the study:

- The protocol
- The Investigator's participation in the study
- Subject recruitment materials (written information or materials including web pages, radio advertisements, television spots or written text developed to encourage subject enrollment)
- The ICF to be used in this study.

Documentation of IRB approval of the study protocol and informed consent must be provided to the Sponsor prior to initiation of the study. In addition, the Investigator must

ensure that the reviewing IRB has provided approval for any protocol amendments prior to implementation. If the amendment necessitates a revision to the ICF, the Investigator should ensure the revised form is also submitted to and approved by the Sponsor and the IRB and implemented as directed.

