Compare high contrast distance lens VA to high contrast VA at Screening/Dispensing Visit			X	X			X	

[figure not shown]
PROCEDURES / ASSESSMENTS	Screening/Dispensing	2-Week Follow-up Visit	1-Month Follow-up Visit	2-Month Follow-up Visit	3-Month Follow-up Visit	Exit Visit	Unscheduled Visit	Post Study Follow-Up Visit
	Day 0	Day 10-18	Day 26-34	Day 53-67	Day 83-97			
Study Materials								
Dispense Lenses (record lens brand, sphere power, base curve); If replacement lens, record reason for replacement	X		X	X			X	
Dispense Study kit bottles 1, 2, 3 and 4 (keep bottle 5 as a reserve at the site);	X							
Dispense Study Kit reserve (Bottle 5, if needed)		X	X	X			X	
Dispense other supplies as needed (see Protocol Section 4.4.3)	X	X	X	X			X	
Collect worn lenses from subject			X	X	X	X	X	
Collect used and unused bottles of study solutions					X	X		
Return study materials to sponsor					X	X		

[figure not shown]
^a At the screening visit, only complete the Exit Form if the subject was randomized.

[figure not shown]
^b Use provided rating scales (separate document).

[figure not shown]
Note: All VA measurements MUST be made using a phoropter.

[figure not shown]
Note: If this is an Exit Visit, also perform the procedures listed under the Exit Visit column.

[figure not shown]

[figure not shown]

[figure not shown]

[figure not shown]

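### The comfort and dryness models leave out lens group, a randomisation stratum, and any baseline score: a loss of precision, not a bias, to be fixed together with the two-eye handling

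*Combined protocol and SAP*

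**What the plan says.** Section 8.4 states: "The randomization will be stratified by lens group within investigational site". There are five lens groups and about 18 sites. The same section aims for at least four lens strata per site, so that site and lens type are not confounded.

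For comfort, Section 8.6.1.2 averages each eye's follow-up scores and sets a one-sided lower 97.5% limit "computed using an analysis of variance model including the fixed factor of treatment and the fixed blocking factor of site". Success means a limit above -5.0. Section 8.6.1.3 adds: "Dryness will be analyzed using the methods described above for overall comfort". Neither model has lens group, a baseline score or a subject term. Section 8.6.1.1 says that "eyes will be treated as independent sampling units in eye level analyses unless otherwise noted", and the comfort and dryness sections note no exception.

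In Section 6.1.1, step f has the subject complete "The Initial Symptoms/Complaints Form (Worn Lenses Symptoms/Complaints Form), including use of rewetting drops". Step j is a shorter symptom form on the new study lenses. Randomisation comes only at step m: "Log into ORS to randomize the subject". Both forms are therefore pre-randomisation. Their rating scales are in a separate document, according to the Appendix A footnote.

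**The concern.** A factor used to stratify randomisation normally belongs in the primary model. The design balances the arms on it, and a model that ignores it counts the between-stratum variance as noise. Here site is kept and lens group is dropped without a reason. A pre-randomisation score on the outcome scale would usually explain more variance still, and none is used.

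What is at stake is precision on two of the four primary endpoints. Sections 8.3.1 and 8.3.2 claim 96.82% and 96.62% power, but only under independent eyes. Once the pairing of eyes is respected, power drops well below those figures. Covariates that cost no extra subjects are then worth having. The drop itself comes from the correlated eyes, not from the missing covariates.

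**Working it through.** **Inputs from the plan.** 226 eyes (113 subjects) per arm, SD 13.9 (comfort) and 14.0 (dryness), true difference 0, margin -5, one-sided 0.025 (Sections 8.3.1, 8.3.2); five lens groups, about 18 sites.

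**Assumed, because the plan gives none.** Between-eye correlation rho; share of variance explained by lens group (R²); correlation r of the baseline score with the subject's mean follow-up score; block size.

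**1. The plan's own figures.** SE = 13.9 × sqrt(2/226) = 1.308; noncentrality 5/1.308 = 3.82 on 450 df. Power is 96.82% for comfort. The same formula with SD 14.0 gives 96.63% for dryness. The stated values reproduce.

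**2. Cost of the omissions on the same units.**
- Lens group: SE ratio 1/sqrt(1 − R²) = 1.010, 1.026, 1.054 for R² of 2%, 5%, 10%.
- Baseline: SE factor sqrt(1 − r²) = 0.954, 0.866, 0.800 for r of 0.3, 0.5, 0.6.
- If lens group explains nothing: at subject level the error df fall from 207 (226 − 2 − 17) to 203. The critical t rises by 0.01% and the simulated SE by 0.4%.

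**3. Why the two eyes come first.** With correlated eyes, the true variance of the difference is (1 + rho) times what the independent-eyes analysis assumes. Its actual one-sided error is 1 − Φ(1.96/sqrt(1 + rho)) = 5.5%, 7.2%, 7.8% for rho of 0.5, 0.8, 0.9. For the subject mean, SD = 13.9 × sqrt((1 + rho)/2). At rho 0.8 this is 13.19, so SE = 13.19 × sqrt(2/113) = 1.754 and power is 81.0%. At rho 0.5 and 0.9 power is 87.4% and 78.8%.

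**4. Simulation for comfort.** 226 subjects in 18 sites, lens group uniform over five, permuted blocks of 4 within each site-by-lens cell, 4,000 trials per setting. Each fit's lower limit is compared with -5.

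One-sided error at a true difference of -5, rho 0.8, R² 5%, r 0.5:

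| Model | Error | Mean SE |
|---|---|---|
| Eye level, site (as planned) | 6.9% | 1.301 |
| Eye level, site + lens group | 7.5% | 1.268 |
| Subject level, site | 2.2% | 1.777 |
| Subject level, site + lens group | 2.6% | 1.733 |
| Subject level, site + lens group + baseline | 2.4% | 1.505 |

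At R² 10% the two eye-level errors are 6.8% and 7.4%. With blocks of 2 the five errors are 7.6%, 7.7%, 2.4%, 2.7%, 2.8%. The Monte Carlo SE is about 0.25 points near 2.5% and 0.4 near 7%.

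Subject-level power at a true difference of 0 (Monte Carlo SE about 0.6 points near 80%):

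| rho | R² | r | Site | + lens group | + baseline |
|---|---|---|---|---|---|
| 0.8 | 2% | 0.3 | 80.3% | 80.8% | 84.3% |
| 0.8 | 5% | 0.5 | 80.6% | 82.1% | 91.4% |
| 0.5 | 5% | 0.5 | 87.3% | 88.5% | 95.6% |
| 0.9 | 5% | 0.5 | 78.8% | 80.2% | 90.1% |

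Repeat runs at rho 0.8, R² 5%, r 0.5 gave eye-level error of 6.2% to 7.3%, subject-level error of 1.6% to 2.2%, and power of 79.6% to 80.7% (site only) and 90.8% to 91.5% (both terms added).

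**5. Bias.** At a true difference of -5 the mean estimate was -5.02 with treatment and site, and -5.01 with lens group and baseline added. The omission does not shift the estimate.

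**The case against.** The strongest objection is that the serious consequence belongs to another defect. The fall from 96.82% comes from treating eyes as independent, and adding lens group to the planned model would raise its error slightly. On that view this is a rider to the eye-independence problem. The attribution is right, and it is why the two changes must be made together. It does not remove the case for the covariates once the eyes are handled properly.

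Second, lens group alone adds only 0.5 to 1.5 power points in the settings above. Nearly all the gain comes from a baseline score whose items cannot be seen. It would concern habitual lenses on the previous care product, and some subjects might arrive without lenses. This stands: the baseline part is conditional, and r is assumed.

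Third, balance on lens group is only approximate. Up to 18 × 5 = 90 cells for 226 subjects is about 2.5 per cell, so many blocks stay incomplete. The conservatism of the site-only subject-level model is therefore slight: a larger run of 20,000 trials gave an error of 2.2% to 2.3%.

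Fourth, absence of bias follows from randomisation, whereas the primary set is Per Protocol (Section 8.5.2). Exclusions after randomisation could bias either model. That caveat applies equally to both.

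Finally, Section 8.6.1.1 defers detail to a separate analysis plan, which may add covariates. But Section 8.6.1.2 ties the success rule to the treatment-and-site model, so a different model there would have to be reconciled with it.

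**Conclusion.** The point holds as a recommended improvement, not a fatal flaw. Lens group is a randomisation stratum missing from both models, and a pre-randomisation symptom form goes unused. The omission costs precision and does not by itself bias the comparison.

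The size depends on assumed values. Lens group alone is worth a few percent of the standard error at most. A baseline score with r of 0.3 to 0.6 is worth 5% to 20%. In a subject-level analysis at rho 0.8, the two together raise comfort power from about 80% to between 84% and 91% in the settings simulated. The dryness SD is almost the same, so the same conclusion applies. Confidence in the baseline part is limited until the form is checked.

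**What to change.** In Sections 8.6.1.2 and 8.6.1.3:

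- Analyse one value per subject (the mean of the two eyes), or keep eye-level data with a subject random effect or subject-clustered standard errors.
- Include treatment, site and lens group as fixed main effects, not the full site-by-lens cross.
- Check the rating scales. If the worn-lens form records the same comfort or dryness item, add that baseline score as a covariate. Check the step j form as well, and name in advance which score is used. If neither has the item, add lens group only.
- State how a missing baseline score is handled, so that adjustment does not drop subjects.
- Do not add these terms to the independent-eyes model on its own.

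A lens-group-stratified interval for deposits is optional. With group rates spread evenly over 10 or 15 points around 0.925, it would cut the SE by only about 1% or 2%. The slit lamp interval can stay unstratified.

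The cost is a small wording change before unmasking, in the protocol or the separate analysis plan, with the two kept consistent. If the protocol is amended, Section 9.6 requires the investigator to "ensure that the reviewing IRB has provided approval for any protocol amendments prior to implementation". Lens group is already collected, and baseline needs no new data if the form holds the items. If lens group explains nothing, the loss is about 0.4% in the SE.
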